5.6.2 Informed consent from the patient

As soon as patients have recovered, information about enrollment in the study is provided to the patient. They are explained that a legal representative has been informed about enrollment in the study.

Patients are explained that information about the clinical course until one year is needed for the study. The patients are also invited to receive a telephone call at 30 days and to fill-out questionnaires on quality of life and work resumption, via e-mail or surface mail.

Patients are asked to sign a written informed consent stating that they agree to fill out questionnaires on quality of life and work resumption (if applicable) and that clinical

information about follow-up beyond hospital discharge is gathered from hospital and general practitioners records. If the patient refuses, no further information beyond hospital discharge is collected. Patients are allowed to discontinue clinical follow-up beyond hospital discharge at any time.

Patients are also informed and asked to give consent to link patient data to existing quality registrations in the Netherlands in order to improve quality of care (the Netherlands Heart Registration (www.nederlandsehartregistratie.nl), the Dutch Hospital Data registration (www.dhd.nl), the Vektis registration (www.vektis.nl) and the NICE registration (www.stichting-nice.nl)). Also, consent to record patient data in the Netherlands Heart Registration is asked in order to answer future scientific issues considering cardiogenic shock.

6. INVESTIGATIONAL PRODUCT

6.1 Investigational product: norepinephrine

Noradrenaline is indicated for use as an emergency measure in the restoration of blood pressure in cases of acute hypotension.

Please find additional information on norepinephrine in the Summary of Product Characteristics of 'Noradrenaline (Norepinephrine) 1 mg/ml Concentrate for Solution for Infusion', that can be found on www.geneesmiddeleninformatiebank.nl.

6.2 Summary of findings from non-clinical and clinical studies

The summary of findings is not relevant for this study as the aim is not to evaluate the use or the effect of norepinephrine itself. Instead, norepinephrine is used in the same manner as is described in the authorised form of the SPC. The aim of the study is to evaluate the effect of less norepinephrine and therefore accepting a lower blood pressure.

6.3 Summary of known and potential risks and benefits

Please find a list of potential risks in paragraph 4.4 of the SPC.

6.4 Description and justification of route of administration and dosage

Please find the route of administration in paragraph 4.2 of the SPC. The noradrenaline therapy dosage is given according to standard of care.

6.5 Low intervention clinical trial

According to the definitions in the EU Clinical Trial Regulation 536/2014, this study assesses standard treatment while posing only a minimal additional risk to subject safety, and therefore should be defined as a low intervention clinical trial. Also the investigational medicinal product (noradrenaline) is already authorised and is only used in accordance with the terms of the marketing authorisation. Due to the character of low intervention studies, and the fact that this trial does not involve blinding of the label, no additional labelling of the product is required.

6.6 Drugaccountability

Patients will be prescribed noradrenaline according with routine clinical practice. Shipment, receipt and dispense of noradrenaline will be performed according to local (pharmacy) protocol. Drug accountability on individual level will be the responsibility of the study team (i.e. by recording batch numbers and expiration date). Information on drug accountability at individual level will be stored in the electronic Clinical Research Form (eCRF).

7. DATA-COLLECTION

7.1 Data collection

The NORSHOCK trial consists of information blocks containing baseline data, information about the PCI procedure, details on the clinical course during hospital admission and clinical events at 30 days. Patients are followed clinically by telephone contact at 30 days after the PCI procedure for neurological scoring. Data required for analysis is obtained as outlined in **Table 1**. For details on data collection during hospital stay, see **table 2**.

7.1.1 Baseline data

The following baseline information, collected at the moment of randomization, is entered into the electronic case report form (eCRF):

- Date of admission
- Age
- Sex
- Weight, height
- Medical history
- Cardiovascular risk factors
- Resuscitation prior to randomization
- Blood pressure, heart rate
- ECG characteristics
- Signs of impaired organ perfusion
- Timing of randomization (before or after revascularization)

7.1.2 PCI procedure

The following information about the PCI procedure is entered into the eCRF:

- The location of the culprit lesion and a complete anatomic description of coronary status (such as presence of single or multivessel disease and lesion severity)
- TIMI flow pre- and post-procedural

	Randomiz ation	ICU stay	30 Days	3 Months	6 Months	1 Year
Eligibility criteria	X					
Demographics (sex, age, weight, height)	X					
Medical history (DM, HT, stroke, prior PCI/CABG, renal failure)	X					
OHCA prior to presentation (yes, no)	X					
ECG (ST-segment elevation resolution)	X	X				
Vitals (blood pressure and heart rate)	X					
CAG characteristics (LAD, RCX, RCA, Main stem, ((significant stenosis, CTO, culprit, treated vessel))	X					
Hourly blood pressure and heart rate		X				
Laboratory testing	X	X				X
Hemodynamic parameters (invasive hemodynamic measurements)	X	X				
Use of vasoactive medication		X				
Renal replacement therapy		X				
Use of mechanical support		X				
Mechanical ventilation		X				
Protocol adherence		X				
Sedative medication		X				
Echocardiography		X				
Adverse events (arrhythmias, (suspected) infection, ...)		X				
Neurological outcome			X			X
Resource utilization (iMCQ+ iPCQ)			X	X	X	X
Left ventricular ejection fraction (LVEF)		X				X
Quality of life (SF-36 + EQ-5D-5L)						X

Table 1.

7.1.3 Laboratory data

The following laboratory data, that are part of routine care unless stated otherwise, are entered into the eCRF (*for details, see table 2*):

- Cardiac enzymes: serial measurements during the first 72 hours for hs-troponine T and CK-MB*.
- Lactate: will be measured at baseline, at 3 and 6 hours after randomization and with larger intervals hereafter.
- Creatinine: serial creatinine-levels during ICU / CCU stay, level at one year
- Other: C-reactive protein, glucose, hemoglobin, leukocytes, nt-proBNP* and blood urea nitrogen will be measured on admission and daily during ICU/CCU stay.

* Not part of routine care in every hospital

	T = 0 (ICU admission)	T = 3	T = 6	T = 12	T = 24	Day 2	Day 3	Day 4
Lactate	X	X	X	X	X	X	X	X
Hb	X				X	X	X	X
Leukocytes	X				X	X	X	X
CRP	X				X	X	X	X
Glucose	X							
Creatinin	X				X	X	X	X
Blood urea nitrogen	X				X	X	X	X
Liver function	X				X	X	X	X
Troponine T(hs)	X		X	X	X		X	
CK-MB	X		X	X	X		X	
Nt-proBNP	X					X		
Hourly blood pressure and heart rate for the first 24h	X	X	X	X	X			
Invasive haemodynamic measurements	X		X	X	X	X		
Urine production					X	X	X	X
Echocardiography							X	
ECG	X		X		X	X	X	X

Table 2.

7.1.4 Hemodynamic parameters

The following data on hemodynamics are entered into the eCRF

- Blood pressure and heart rate (hourly for the first 24 hours)
- Invasive hemodynamic measurements (every 8 hours during the first 48 hours)

7.1.5 Clinical data

The following information about clinical events is entered into the eCRF:

- Mortality (at 30 days, 1 year)
 - Cardiovascular
 - All-cause
- Severe renal failure requiring renal replacement therapy (at 30 days, 1 year)
- Length of ICU stay
- Length of hospital stay
- (Duration of) mechanical ventilation
- (Duration of) mechanical circulatory support
- Time to hemodynamic stabilization
- (Duration of) catecholamine therapy
- Vasoactive inotropic score
- Arrhythmias during admission
- Major vascular complication during admission (bleed or thrombo embolic event)
- Infection / sepsis during admission
- Myocardial re-infarction within 30 days
- Left ventricular ejection fraction (at 3 days, before hospital discharge and at 1 year)
- Neurological outcome (at 30 days and 1 year)
- Protocol adherence / use of bail-out therapy
- Hospital readmission for cardiac reason within 1 year

7.1.6 Cost-effectiveness

Data on quality of life is collected through questionnaires at 30 days, 3 months, 6 months and 1 year. This does not require a hospital visit.

8. STUDY ENDPOINTS

8.1 Primary endpoint

The primary endpoint of the study is the composite of all-cause mortality and severe renal failure requiring renal replacement therapy within 30 days after randomization.

8.2 Ranked secondary endpoints *(for definitions, see Appendix A)*

The ranked secondary endpoints are:

- All-cause mortality at 30 days
- Days alive and out of hospital (30 days)

8.3 Tertiary endpoints *(for definitions, see Appendix A)*

The tertiary endpoints are:

- Days alive and out of ICU (30 days)
- Cardiovascular death at 1 year
- Enzymatic infarct size
- Lactate clearance (mean + area under the curve 0-36 hours)
- Days alive and free of mechanical ventilation (30 days)
- Days alive and free of mechanical circulatory support (30 days)
- Severe renal failure requiring renal replacement therapy (at 30 days, 1 year)
- Renal function (during hospital stay and 1 year)
- Time to peak creatinine (hospital stay)
- Time to renal replacement therapy
- Days alive and free of catecholamine therapy (30 days)
- Vasoactive inotropic score (VIS) (during hospital stay)
- Time to hemodynamic stabilization (hospital stay)
- Blood pressure and heart rate during the first 24 hours
- Hemodynamic parameters (during ICU / CCU admission)
- Arrhythmias during hospital admission
- Major vascular complication during admission (bleed or thrombo embolic event)
- Infection / sepsis during hospital admission
- Myocardial re-infarction within 30 days
- Left ventricular ejection fraction (at day 3, before hospital discharge, and at 1 year)

- Neurological outcome (at 30 days and 1 year)
- Protocol adherence / use of bail-out therapy
- Hospital readmission for cardiac reason within 1 year

The cost-effectiveness endpoints are:

- Health-related quality of life based on the EQ-5D-5L questionnaire at 12 months
- Resource utilization based on iMTA Medical Consumption (iMCQ) and iMTA Productivity Cost Questionnaire (iPCQ) (at 30-day, 3-month, 6-month and 1-year follow-up)

9. STATISTICAL ANALYSIS

9.1 General methods

All descriptive statistical analyses are performed using SPSS statistical software (IBM Corp., Armonk NY, version 28.0 or higher), unless otherwise noted.

In general, continuous variables are summarized using descriptive statistics including means and standard deviations if normally distributed or median with interquartile ranges for skewed distributions. Discrete variables are summarized using absolute and relative frequencies. Demographic and baseline characteristics are summarized by randomized regimen group and for all randomized patients combined.

9.2 Main analysis of the primary endpoint and ranked secondary endpoints

The following hypotheses are tested in a hierarchical order, to preserve type I error rate:

1. A lower MAP-target regimen (≥ 55 mmHg) is non-inferior to the standard MAP-target regimen ($\text{MAP} \geq 65$ mmHg) in terms of the primary endpoint of the composite of all-cause mortality and severe renal failure at 30 days.
2. A lower MAP-target regimen (≥ 55 mmHg) is superior to the standard MAP-target regimen ($\text{MAP} \geq 65$ mmHg) in terms of the primary endpoint of the composite of all-cause mortality and severe renal failure at 30 days.
3. A lower MAP-target regimen (≥ 55 mmHg) is superior to the standard MAP-target regimen ($\text{MAP} \geq 65$ mmHg) in terms of the first secondary endpoint of all-cause mortality at 30 days.
4. A lower MAP-target regimen (≥ 55 mmHg) is superior to the standard MAP-target regimen ($\text{MAP} \geq 65$ mmHg) in terms of the second secondary endpoint of days alive and out of hospital at 30 days.

All analyses are performed on an intention-to-treat (ITT) basis. The ITT population consists of all subjects who have been randomized (i.e. when the subject number and allocated regimen are recorded in the electronic case report form (eCRF)). Patients are analysed in accordance with the randomized treatment assignment irrespective of the factual implementation of the assigned treatment regimen.

Rates of primary and first secondary endpoint are estimated as the cumulative incidence at 30 days after randomization by the Kaplan-Meier method. Rate differences are defined as the rate in the index group minus the rate in the reference group.

1. Non-inferiority of the lower MAP-target regimen in terms of combined all-cause mortality and severe renal failure at 30 days is declared if the upper limit of the 95% confidence interval (CI) of the rate difference excludes 10%. This is the equivalent of non-inferiority testing with a one-sided alpha of 0.025 with a non-inferiority limit of 10%.
2. Superiority of the lower MAP-target regimen in terms of combined all-cause mortality and severe renal failure at 30 days is declared if the 95% confidence interval (CI) of the rate difference excludes 0%. This is the equivalent of superiority testing with a 2-sided alpha of 0.05.
3. Superiority of the lower MAP-target regimen in terms of all-cause mortality at 30 days is declared if the 95% confidence interval (CI) of the rate difference excludes 0%. This is the equivalent of superiority testing with a 2-sided alpha of 0.05.
4. Superiority of the lower MAP-target regimen in terms of days alive and out of hospital at 30 days is declared if the two-sided p-value of the Mann-Whitney-U test applied to days alive and out of hospital at 30 days is lower than 0.05.

Details of the statistical analyses will be provided in the statistical analysis plan.

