5. TREATMENT AND FOLLOW-UP

5.1 Randomization and treatment allocation

Patients are randomized either at the catheterization laboratory (before or after revascularization by PCI) or at the ICU / CCU up to a maximum of 2 hours after PCI, as soon as the treating physician has established the diagnosis of CS (*see criteria above*). As patients are in immediate need of treatment with noradrenaline, patients are randomized without preceding informed consent (*see section 5.6*).

Patients meeting the selection criteria are randomized in a 1:1 ratio to index regimen, with a MAP-target of ≥ 55 mmHg, or reference regimen, with a standard MAP-target. A web based randomization program with stratification per center is used. The randomized regimen is started immediately after randomization.

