9.3 Determination of sample size

The rate of the primary endpoint in the reference group was estimated from the culprit-shock trial, where the event rate was 45.9%.[3] No other study ever tested the same intervention but from experimental myocardial infarction studies we have learned that the administration of noradrenaline is associated with infarct size expansion up to 22%.[12] Besides that, patients with high noradrenaline levels after myocardial infarction have a 4 times higher mortality rate compared with those without high noradrenaline levels.[13] On the basis of the much higher death rate and larger infarct size, we hypothesize that the event rate of the primary endpoint under the lower MAP-target regimen might be 10% lower than that under the standard MAP-target regimen. These assumptions form the basis for the sample size calculation for superiority testing of the primary endpoint. For non-inferiority testing we took a non-inferiority margin of 10%, equivalent to the inverse of the above mentioned treatment benefit.

We calculated that with 752 evaluable patients, the study has 80% power to show superiority of the lower MAP-target regimen (versus the standard MAP-target regimen) under the above mentioned design assumptions, with rates of the primary endpoint of 45.9% under the standard MAP-target regimen and of 35.9% under the lower MAP-target regimen.

We further calculated that with 752 evaluable patients, the study has 79% power to show non-inferiority of the lower MAP-target regimen (versus the standard MAP-target regimen) with a non-inferiority margin of 10% and event rates of the primary endpoint of 45.9% in both treatment regimens.

To allow for attrition rate of 3%, 776 (2 x 388) patients will be randomized.

Sample size calculation is made using PASS Sample Size Software, version 13.

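### The primary contrast is fixed as a crude Kaplan-Meier rate difference: valid and consistent with the sample size, but it forgoes precision that recorded baseline variables could give, notably for a non-inferiority test planned at 79% power

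*Protocol*

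**What the plan says.** Protocol section 9.2 sets the estimator: "Rates of primary and first secondary endpoint are estimated as the cumulative incidence at 30 days after randomization by the Kaplan-Meier method". It then sets the contrast: "Rate differences are defined as the rate in the index group minus the rate in the reference group". The 95% confidence interval of that difference is compared with 10% for non-inferiority and with 0% for superiority on the primary endpoint. The same 0% rule applies to 30-day mortality. No stratum or covariate is named. How the interval is computed is not stated, and the section leaves further detail to the statistical analysis plan.

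Section 5.1 describes the allocation: "A web based randomization program with stratification per center is used". Section 7.1.1 lists what is recorded at randomisation, including age, medical history, blood pressure, signs of impaired perfusion and "Resuscitation prior to randomization". Table 1 includes renal failure in the medical history. Several of these variables return in section 9.5, but only to define subgroups.

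Section 9.3 plans 752 evaluable patients for 80% superiority power, "with rates of the primary endpoint of 45.9% under the standard MAP-target regimen and of 35.9% under the lower MAP-target regimen". It states 79% non-inferiority power at 45.9% in both arms, and 776 randomised after 3% attrition.

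**The concern.** When allocation is stratified and baseline variables predict the outcome, an analysis that uses them usually gives a narrower interval for the same treatment effect. Here the stratum and several plausible predictors are available, and the confirmatory contrast uses none of them.

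What is at stake is precision. Non-inferiority on the primary endpoint is tested first, and a failure there ends the sequence. If the two regimens have the same event rate, it is the only positive claim the trial can properly reach, and that is the scenario for which the protocol gives 79% power.

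The deferral to the analysis plan does not fully settle the matter. It leaves the interval method open, but section 9.2 already fixes the point estimate and the contrast. An analysis plan that made an adjusted risk difference primary would depart from the protocol.

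**Working it through.** **Inputs.** From section 9.3: event rates of 45.9% and 35.9%, and 752 evaluable patients, so 376 per arm at the 1:1 ratio of section 5.1. From section 9.2: two-sided alpha 0.05, one-sided alpha 0.025 and a margin of 10 points, so z = 1.96 in both cases. R², the share of outcome variance explained by centre and baseline variables, is not in the documents and is assumed over a range.

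**Step 1: reproduce the protocol's figures on the crude contrast.**

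- Superiority: SE = √[(0.459 × 0.541 + 0.359 × 0.641)/376] = 0.0357. Power = Φ(0.10/0.0357 − 1.96) = 80.1%. Solving the same unpooled formula for 80% power gives 752 in total.
- Non-inferiority: SE = √[2 × 0.459 × 0.541/376] = 0.0363. Power = Φ(0.10/0.0363 − 1.96) = 78.6%, against the stated 79%.
- Attrition: 752/0.97 = 775.3, rounded up to 776.

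All three agree, so the sample size was built for the unadjusted analysis.

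**Step 2: effect of adjustment.** Multiply each SE by √(1 − R²). For example, at R² 0.10 the superiority SE is 0.0357 × 0.949 = 0.0338, and power is Φ(0.10/0.0338 − 1.96) = 84.0%.

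| Assumed R² | 95% CI half-width (superiority scenario), points | Superiority power | Non-inferiority power (equal rates) |
|---|---|---|---|
| 0 | 7.0 | 80.1% | 78.6% |
| 0.02 | 6.9 | 80.8% | 79.4% |
| 0.05 | 6.8 | 82.0% | 80.6% |
| 0.10 | 6.6 | 84.0% | 82.6% |
| 0.20 | 6.3 | 88.0% | 86.8% |

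**Step 3: simulation check.** 2,000 trials were run per setting with 752 patients, 12 centres (assumed), allocation balanced within centre and complete 30-day follow-up, in which case Kaplan-Meier equals the simple proportion. The crude difference was compared with a standardised logistic risk difference.

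- Centre only (assumed between-centre SD 0.3 on the logit scale, R² about 0.02): SE 0.0356 for both methods in the superiority setting. Superiority power was 78.9% crude and 79.2% adjusted; non-inferiority power was 79.5% and 80.0%.
- With a prognostic score added, R² 0.07: superiority 81.4% to 84.1%, non-inferiority 78.0% to 81.2%.
- R² 0.18: superiority 81.6% to 87.5%, non-inferiority 78.7% to 87.1%.
- Error rates, crude analysis: two-sided 4.3% to 5.6% under equal rates, and false non-inferiority 2.1% to 2.8% at a true excess of 10 points.
- Error rates, adjusted analysis: 4.3% to 6.1% and 2.1% to 2.9%. The 6.1% arose at R² 0.30, where the crude analysis gave 5.6% on the same data. The Monte Carlo standard error at 5% is about 0.5 points (√(0.05 × 0.95/2000)).

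**Step 4: non-inferiority under the design alternative.** At 35.9% against 45.9% the true difference lies 20 points from the margin. Power = Φ(0.20/0.0357 − 1.96), which exceeds 99.9%.

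**The case against.** The strongest reply is that nothing here is wrong. The crude contrast is a valid intention-to-treat analysis, its simulated error rates are close to nominal, and the sample size was computed for it. All of that stands, and it makes this an efficiency point.

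Four stronger readings are tempting, and the documents do not support them.

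- A reader might infer that leaving out the stratification factor makes the interval materially too wide. The protocol gives neither the number of centres nor the variation between them, and under the assumed spread centre alone changes almost nothing.
- A reader might infer a large loss because the baseline variables are strong predictors. Their strength is not documented. At R² 0.02 the gain is under 1 point.
- A reader might infer that the plan has no reserve. The 79% applies only when both rates are 45.9%; under the design alternative non-inferiority is almost certain. Nor does the non-inferiority gate cost any superiority power: a favourable interval that excludes 0% necessarily excludes 10%.
- A reader might infer that the crude contrast saves nothing. It avoids a working model, a choice of covariates, sparse centres and missing baseline values.

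A further objection bears on the remedy. Under section 5.6.2, a patient who refuses consent contributes nothing after hospital discharge, so some follow-up can end before day 30. Kaplan-Meier accommodates this and a plain binary regression does not. The objection stands, and it shapes the fix. The power figures above also ignore such censoring.

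**Conclusion.** The point holds as an inexpensive improvement to a valid analysis. Section 9.2 fixes a crude contrast where a standardised one would estimate the same marginal 30-day difference against the same limits, probably with more precision. The gain in power at 752 patients runs from under 1 point at R² 0.02 to about 8 points at R² 0.20 (88.0 − 80.1 = 7.9 for superiority; 86.8 − 78.6 = 8.2 for non-inferiority). At R² 0.05 non-inferiority power already passes 80%.

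These figures rest on assumed R² values, on the protocol's event rates and on complete 30-day follow-up. Almost all of the gain would come from the prognostic covariates. It should be treated as extra assurance and not as grounds for a smaller sample, since R² is unknown.

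**What to change.** Amend section 9.2, with matching text in the statistical analysis plan, before any comparative data are seen.

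- **Estimator:** make the primary estimate a covariate-standardised marginal 30-day risk difference that handles censoring before day 30. Options are standardised risks from a survival model, regression on Kaplan-Meier pseudo-values, or regression with inverse-probability-of-censoring weights. Use a robust or bootstrap 95% confidence interval, and check by simulation that it holds its level with many small centres. Apply the same approach to 30-day mortality.
- **Covariates:** centre, with small centres pooled, plus age, resuscitation before randomisation, baseline MAP and history of renal insufficiency. Use only values measured before randomisation.
- **Lactate:** leave it out unless it is drawn before randomisation. Table 2 labels T = 0 as ICU admission, while section 5.1 allows randomisation earlier, in the catheterization laboratory.
- **Unchanged:** the 10% and 0% limits, the hierarchy and the sample size. Keep the crude Kaplan-Meier difference as a sensitivity analysis.

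The cost is wording, because the named variables are already collected. The small downside is a working model, a rule for pooling centres and a rule for missing baseline values, all to be stated in advance.
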